b Note that weight assessment is included in the vital signs assessment module in the eCRF instead of the physical examinations module. Nevertheless, it is to be performed at baseline and on yearly basis and not every 6 months.

c If not performed in the previous 6 months.

d If the HRUQ questionnaire was administered in the previous 3 months, then only questions 1 through 9 of the Modified HRUQ/HRPQ need to be completed at baseline.

e For consenting patients only.

f Omit if collected at a previous visit.

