### **9.6.3 Brain imaging**

Brain imaging will be performed at D1 (if not performed in the previous 6 months) and then every 12 months. It will be also performed at the end of study visit, if not performed in the previous 6 months. MRIs will be read and interpreted locally by qualified site personnel and/or designee (eg, neuroradiologist). MRIs should be reviewed locally by qualified site personnel for signs of Non-MS pathology. For study purposes, per-protocol scans will be also submitted to a central imaging vendor for scan quality control and analysis.

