#### **9.6.3.3 MRI-T2**

The total MRI T2 lesion volume has been used as a surrogate marker of disease activity in the beta-interferon studies. T2-weighted MRI assessments will also include proton density and fluid attenuated inversion recovery (FLAIR) sequences. The inflammatory demyelination and edema characteristic of active MS lesions as well as the sclerotic gliosis of end-stage MS plaques contribute to the MRI T2 lesion volume, which thus reflects the "burden of disease" in these patients.

Cerebral volume is also estimated from MRI-T2/PD acquisitions to quantify global neuro-degeneration, which is largely due to axonal loss in MS. In this study the rate of cerebral atrophy will be determined from the MRI T2/PD brain scans as changes in the BPF.

The number of new or enlarging hyperintense lesions as detected by T2 weighted MRI has been used as a surrogate marker of efficacy in recent MS studies.

#### 9.6.4 MOS 36-item short-form health survey (SF-36) Version 2

The SF-36 is a self-administered questionnaire designed to assess generic Health Related Quality of Life (HRQoL) in healthy and ill adult populations. The SF-36 consists of 36 items organized into the 8 scales shown below (see [Table 1](#)). The SF-36 also yields 2 summary measures of physical health (the Physical Component Summary [PCS]) and mental health (the Mental Component Summary [MCS]) derived from scale aggregates. Higher global scores are associated with better quality of life.

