## 2 STATISTICAL AND ANALYTICAL PROCEDURES

### 2.1 ANALYSIS ENDPOINTS

#### 2.1.1 Demographic and baseline characteristics

The TOPAZ baseline value is defined as the available value assessed on or prior to the V01 Selection visit, unless otherwise specified. The last available value in previous studies can be considered as the baseline if they were evaluated within the pre-specified time window. For brain imaging result, if the last non-missing assessment performed within 6 months prior to the V01 selection visit, it can be considered as baseline. For vital sign, physical examination, EDSS and questionnaires, the time window is 3 months.

For efficacy endpoints (EDSS, MRI), the baseline from prior studies will be considered as long-term baseline, which is defined as last available assessment prior to first dose of alemtuzumab or SC IFNB-1a administration.

All baseline safety and efficacy parameters (apart from those listed below) are presented along with the on-treatment summary statistics in the safety and efficacy sections ([Section 2.4.5](#) and [Section 2.4.4](#)).

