#### **2.1.3.3.1 Number of lesions**

The cumulative count is the primary interest, which is defined as the sum of the lesion counts at each successive year from the D1 screening to the end of study. The lesion counts will also be analyzed yearly.

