#### **2.4.4.1.5 MRI volume and BPF**

The observed value, change from baseline as well as percentage change from baseline will be presented descriptively.

The percent change in lesion volume / BPF from year to year and the percent change from long-term baseline will be calculated by analysis groups. To compare between IAT and DAT patients, the percent change from baseline in MRI lesion volume will be analyzed yearly using the ranked analysis of covariance (ANCOVA) model with adjustment for baseline lesion volume, analysis groups (IAT and DAT) and geographic region.

Similar analysis for MRI volume by alemtuzumab courses and for retreated population will be analyzed as well.

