### **2.5.3 Windows for time points**

This D1 selection visit must be conducted within 3 months (6 months for US) after completion of the Extension Study CAMMS03409. When possible, the visit will be performed at the same time as the last visit of the Extension Study CAMMS03409. For the follow-up visits, the protocol specified time window is  $\pm 14$  days of target dates for the post-baseline scheduled visits. The target dates for the scheduled visits are based on the calendar date of the D1 selection. All scheduled visits including those that occurred outside the specified windows will be included in the efficacy analysis.

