### **2.5.3.2 Algorithm for Determining Analysis Visit Windows for Efficacy Observations**

For the efficacy assessment, the reference date for the derivation of relative days of events or findings will be D1 selection visit.

Selected efficacy variables will be summarized by the following analysis window:

- EDSS (assessed every 6 months from TOPAZ Day 1 to TOPAZ Month 60, at End of Study (EOS) visit, and at unscheduled visits.)
- SF-36, FAMS and EQ-5D (assessed yearly from TOPAZ Day 1 to TOPAZ Month 60, and at End of Study (EOS) visit.)
- MRI assessments (assessed yearly from TOPAZ Day 1 to TOPAZ Month 60, and at End of Study (EOS) visit.)

The algorithm for determining analysis visit windows and the observations to be used in the safety analyses will be applied to the above efficacy assessments in a similar manner. For efficacy analyses, all visits up to the end of the study, including those outside the protocol specified windows will be included.

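### Year-to-year MRI changes are not divided by scan-to-scan time, although the first interval can be 12 to 18 months and the last about 6

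*Protocol*

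**What the plan says.** **Baseline scan.** Protocol 9.6.3 states: "Brain imaging will be performed at D1 (if not performed in the previous 6 months) and then every 12 months". The flow chart in Protocol 1.2.1 carries the same condition in footnote c ("If not performed in the previous 6 months") and applies it to both the D1 scan and the EOS scan. SAP 2.1.1 turns the D1 waiver into an analysis rule for imaging: "if the last non-missing assessment performed within 6 months prior to the V01 selection visit, it can be considered as baseline".

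**Timing of later scans.** SAP 2.5.3 says: "The target dates for the scheduled visits are based on the calendar date of the D1 selection". For efficacy windows, SAP 2.5.3.2 adds that "the reference date for the derivation of relative days of events or findings will be D1 selection visit". Neither refers to the date of the baseline scan.

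**End of study.** Under Protocol 1.1 and 10.1.4, once five years have passed since the first inclusion, a patient's next six-monthly visit becomes the EOS visit. It can therefore fall at a half-year point such as M54.

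**Analysis.** SAP 2.4.4.1.5 calls for "The percent change in lesion volume / BPF from year to year" and, separately, for percent change from the long-term (pre-treatment) baseline. SAP 2.1.3.3.2 defines percent change as a difference over the baseline value, with no time term. SAP 2.1.3.3.1 makes the cumulative lesion count the main interest and adds: "The lesion counts will also be analyzed yearly". The count model in SAP 2.4.4.1.4 adjusts for long-term baseline count, group and region, and has no offset for time. Protocol 9.6.3.3 says that "the rate of cerebral atrophy will be determined from the MRI T2/PD brain scans as changes in the BPF".

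**The concern.** The age of the baseline scan adds to the first interval and to no other. A patient scanned five months before D1 and again at M12 contributes 17 months of change to a figure labelled Year 1; the Year 2 figure covers a nominal 12. At the other end, an EOS scan soon after an annual scan gives a short last interval. If atrophy proceeds at a steady pace, the undivided series can show a larger first-year loss and a smaller last-year loss with no change in the disease.

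Change over time in brain imaging is a secondary endpoint, and year-to-year change is an output that the SAP specifies in its own right. The pattern matters because a series that flattens after Year 1 could be read as stabilisation during long-term follow-up. The SAP already deals with unequal observation time for relapses: SAP 2.4.4.1.1 uses log follow-up time as the offset. The imaging sections have no counterpart.

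**Working it through.** The documents give no expected MRI rate, scan-age distribution or planned imaging precision, so there is no stated figure to reproduce. The check is interval arithmetic under an assumed constant (linear) true rate.

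**Inputs**
- Age of the baseline scan at D1: a = 0 to 6 months (Protocol 1.2.1 footnote c and 9.6.3; SAP 2.1.1).
- Annual scans at 12-month steps from D1, each ±14 days (Protocol 10.1.3; SAP 2.5.3). In months, 14/30.4375 = 0.46.
- EOS at a six-monthly visit, with a scan only if none was done in the preceding 6 months (Protocol 1.1, 9.6.3 and 10.1.4).

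**Interval lengths**
- First interval: 12 + a, so 12 to 18 months nominally. With the M12 window: 12 − 0.46 = 11.5 to 18 + 0.46 = 18.5.
- Later annual intervals: 12 months nominally. With both windows: 12 ± 0.92, so 11.1 to 12.9.
- Last interval, with EOS at M54 and a scan done there after one at M48: about 6 months.

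**Effect on a raw change**

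Ratio of Year 1 to a later year = (12 + a)/12. Apparent fall after Year 1 = 1 − 12/(12 + a). Ratio for a change or sum from D1 to M60 = (60 + a)/60.

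| a (months) | First interval | Year 1 ratio | Apparent fall | D1 to M60 ratio |
|---|---|---|---|---|
| 0 | 12 | 1.00 | 0% | 1.00 |
| 1 | 13 | 1.08 | 7.7% | 1.02 |
| 3 | 15 | 1.25 | 20% | 1.05 |
| 6 | 18 | 1.50 | 33% | 1.10 |

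For a 6-month last interval the ratio is 6/12 = 0.50.

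For scale, take an assumed steady BPF loss of 0.20% per year. At a = 6, Year 1 would show 0.20 × 1.50 = 0.30% and a full later year 0.20%, a difference of 0.10 percentage point.

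**Group means.** Suppose a share p of patients reuse a scan, with ages spread evenly over 0 to 6 months (mean 3). Both are assumptions. The mean first interval is 12 + 3p:
- p = 25%: 12.75 months, ratio 1.06, fall 5.9%.
- p = 50%: 13.5 months, ratio 1.13, fall 11.1%.
- p = 100%: 15 months, ratio 1.25, fall 20%.

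**What is not affected**
- Percent change from long-term baseline at M12 and later. Neither end of that comparison is the D1 scan. Only the D1 point itself is affected, by at most 6/72 = 8% of the change accrued, taking 2 + 4 prior years from SAP 1.4 and a constant rate.
- Counts of Gd-enhancing lesions present on a scan, which do not depend on when the previous scan was done.

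**What depends on an undefined rule.** New-lesion counts, yearly or cumulative, follow the ratios above only if each scan is judged against the previous one. The documents do not name the comparison scan.

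**After correction.** Dividing each change by its own interval gives r(12 + a)/(12 + a) = r, the same as any later year. Under a constant rate the artefact is zero for every a.

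**The case against.** The strongest reply is that the weight of the imaging analysis lies elsewhere. SAP 2.4.4 makes IAT versus DAT the main long-term comparison and refers it to the pre-treatment baseline, which the reused scan does not touch. No planned analysis tests Year 1 against later years, and Protocol 11.4 foresees no formal hypothesis tests. Scan age may also be small. Protocol 10.1.1 wants D1 to coincide with the last extension visit where possible and otherwise within 3 months (6 in the US). If the last extension scan was taken at that final visit (an assumption), a is at most about 3 outside the US and the ratio at most 1.25. Finally, Protocol 9.6.3.3 equates the atrophy rate with changes in BPF and does not explicitly promise a per-year quotient.

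Most of this stands, and it limits the scope. It does not remove the point, because year-to-year change is a separately specified output with no time term.

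A reader might infer three stronger things that the documents do not support:
- *That the plan will produce a false slowing after Year 1.* It can. The size runs from nil upwards with an unknown scan age, and later intervals are 12 months only nominally. For lesion volume the direction also depends on whether volume is rising or falling: a longer interval enlarges the change in either direction.
- *That the IAT-versus-DAT comparison is biased.* Both groups follow the same scan rule, and nothing indicates different scan ages.
- *That the yearly interim loses the protection of the long-term baseline* because SAP 3 restricts it to TOPAZ data. Read that literally, the same restriction would exclude a reused extension-study scan, so it does not settle the matter.

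**Conclusion.** The point holds for the year-to-year summaries. Raw change in BPF and lesion volume can differ between years through interval length alone: Year 1 by a factor of 1.00 to 1.50 relative to a nominal 12-month year, and the last interval by a factor of about 0.5 where EOS falls at M54 after an M48 scan. New-lesion counts are exposed in the same way, conditionally on how new is defined; a D1-to-M60 sum would cover at most 66 months instead of 60 (+10%), and only in patients who reach M60.

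These figures assume a constant true rate. Where a group falls in the range depends on scan ages that the documents do not give; with the illustrative mix above, the apparent fall in group means is 6% to 20%. The primary safety objective and change from long-term baseline at M12 and later are not at risk. This is a secondary, largely descriptive display, but the correction is cheap and worth making before the yearly results are read as a trend.

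**What to change.** - **SAP 2.4.4.1.5:** report year-to-year change in BPF and lesion volume annualised, that is, divided by the years between the two actual scan dates. Leave percent change from long-term baseline as it is.
- **SAP 2.4.4.1.4:** state which earlier scan defines a new lesion. For new-lesion counts, use log scan-to-scan time as the offset in the negative binomial model, or as the denominator in descriptive tables; for the cumulative count, use the total scan-to-scan time covered. Do not apply this to counts of Gd-enhancing lesions present on a scan.
- **SAP 2.1.1:** define the TOPAZ imaging baseline date as the date of the scan, not of D1, and report the distribution of scan age at D1.

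The cost is SAP wording and one derived variable. The date of a reused scan has to be known already to apply the 6-month rule, so no new scans are needed. The downside is that annualised values from a short last interval are noisier: dividing by half a year doubles the measurement error. Showing the interval length beside them makes this visible.

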### 3 LIST OF ABBREVIATIONS

|       |   |
|-------|---|
| AE:   | adverse events                              |
| AESI: | adverse events of special interest          |
| ARR:  | annualized relapse rate                     |
| BPF:  | brain parenchymal fraction                  |
| CI:   | confidence intervals                        |
| CNS:  | central nervous system                      |
| DMT:  | disease modifying treatment                 |
| EDSS: | expanded disability status scale            |
| EOS:  | end of study                                |
| FAMS: | functional assessment of multiple sclerosis |
| Gd:   | gadolinium                                  |
| HLA:  | human leukocyte antigen                     |
| HLH:  | hemophagocytic lymphohistiocytosis          |
| HPV:  | human papilloma virus                       |
| HRPQ: | health related productivity questionnaire   |
| HRUQ: | health resources utilization questionnaire  |
| IAR:  | infusion-associated reaction                |
| IB:   | investigator's brochure                     |
| ICF:  | informed consent form                       |
| IMP:  | investigational medical product             |
| ITP:  | immune thrombocytopenic purpura             |
| LFT:  | liver function tests                        |
| MOS:  | medical outcome study                       |
| MS:   | multiple sclerosis                          |
| NFD:  | nephrogenic fibrosing dermopathy            |
| NSF:  | nephrogenic systemic fibrosis               |
| PGx:  | pharmacogenomics                            |
| QoL:  | quality of life                             |
| SAE:  | serious adverse events                      |
| SAP:  | statistical analysis plan                   |
| SC:   | subcutaneous                                |
| SNP:  | single nucleotide polymorphism              |
| UK:   | United Kingdom                              |

## 4 INTRODUCTION AND RATIONALE

Multiple sclerosis (MS) is a demyelinating disease of the central nervous system (CNS) that affects approximately 2.5 million people worldwide (1). Its clinical course is typically characterized by initial episodes of transient neurological compromise with full recovery, followed by a phase of cumulative deficits that may increase with each new episode. Most relapsing patients eventually develop secondary progression leading to a constellation of chronic sequelae including profound muscle weakness, impaired gait and mobility, bladder and bowel dysfunction, and cognitive and visual impairments.

MS is believed to arise from the interplay of polygenic inherited susceptibility and as yet unidentified environmental agents. Age of onset typically ranges from 10 to 59 years, with most cases occurring between 20 and 40 years of age. As with most other autoimmune disorders, MS is more than twice as common among women. Pathologically, MS is characterized by focal and non-focal tissue injury of the brain and spinal cord due to the complex interplay of inflammation, demyelination, axonal injury, astrogliosis, and tissue atrophy. Lymphocytes are believed to play a central role in MS pathogenesis.

Alemtuzumab (Lemtrada®) is a humanized monoclonal antibody that binds to CD52, a cell surface antigen present at high levels on T and B lymphocytes, and at lower levels on natural killer cells, monocytes, and macrophages (2).

There is little or no CD52 detected on neutrophils, plasma cells, or bone marrow stem cells. Alemtuzumab acts through antibody-dependent cellular cytotoxicity and complement mediated lysis following cell surface binding to T and B lymphocytes.

The mechanism by which alemtuzumab exerts its therapeutic effects in MS is unknown, but may involve immunomodulation through the depletion and repopulation of lymphocytes.

Research suggests that potential immunomodulatory effects in MS may include alterations in the number, proportions, and properties of some lymphocyte subsets post-treatment (3).

Pilot studies in MS patients were conducted at Addenbrooke's Hospital in the United Kingdom (UK). Genzyme Corporation (Genzyme, a Sanofi company) has sponsored Phase 2 and Phase 3 randomized, comparator-controlled studies in patients with relapsing remitting MS that have established superior efficacy for alemtuzumab compared with subcutaneous interferon beta-1a (SC IFNB-1a, Rebif®) on clinical and imaging endpoints (4, 5, 6, 7, 8).

Identified risks of alemtuzumab in patients with MS include:

- Infusion-associated reactions (IAR)
- Serious infections
- Autoimmunity (notably, Immune thrombocytopenic purpura (ITP), thyroid dysfunction and nephropathies)

The most important adverse reactions are autoimmunity (eg, ITP, thyroid disorders, nephropathies, cytopenias), IARs, and serious infections. The most common adverse events

reported after alemtuzumab treatment (in  $\geq 20\%$  of patients) are rash, headache, pyrexia, and respiratory tract infections. Of note, Listeriosis/Listeria meningitis has been reported in LEMTRADA treated patients, generally within one month of LEMTRADA infusion. To reduce the risk of infection, patients receiving LEMTRADA should avoid ingestion of uncooked or undercooked meats, soft cheeses and unpasteurized dairy products two weeks prior to, during, and for at least one month after LEMTRADA infusion.

The Sponsor has conducted a comprehensive review of safety data from post-marketing use of alemtuzumab and added the following to the current list of AESIs:

- Autoimmune hepatitis
- Acquired hemophilia A
- Hemophagocytic lymphohistiocytosis (HLH)
- Progressive multifocal leukoencephalopathy (PML)
- Temporally associated\* pulmonary alveolar hemorrhage
- Temporally associated\* myocardial ischemia, myocardial infarction
- Temporally associated\* stroke
- Temporally associated\* cervicocephalic arterial dissection

\* Temporally associated: 1 to 3 days after the last infusion

Cases of serious and life-threatening stroke (including hemorrhagic and ischemic), myocardial infarction and cervicocephalic (ie, vertebral, carotid) arterial dissection have been reported within three days of alemtuzumab administration, with most cases occurring within one day. Cases of pulmonary alveolar hemorrhage have been reported with onset within 48 hours of alemtuzumab infusion. Long term auto immune risks, such as cases of Hemophagocytic lymphohistiocytosis (HLH) and autoimmune hepatitis causing clinically significant liver injury, including acute liver failure requiring transplant, has been reported. To minimize the risk of these serious adverse events, recommendations are provided for infusion related management and long term safety monitoring for patients receiving re-treatment of alemtuzumab during the course of the trial:

- Pre infusion: assess overall health status and risk factors; baseline BP/HR, bleeding risk, platelets count. Baseline liver function test.
- During infusion: continuous or hourly monitoring BP/HR; intermittently ambulation, compressive stocking.
- Post infusion: inform/remind patient any abnormal clinical sign/symptoms related to infusion.
- Periodic liver function test.

Please refer to [Section 10.1.6](#) for details.

Study CAMMS03409 is an open-label extension study designed to provide additional safety monitoring for up to 60 months, and as-needed alemtuzumab retreatment to qualifying patients who received alemtuzumab in prior Genzyme-sponsored studies CAMMS223, CAMMS323 and CAMMS324. In addition, patients who received SC IFNB-1a in the earlier studies had the opportunity to receive 2 annual courses of alemtuzumab, and possibly subsequent as-needed alemtuzumab retreatment.

In CAMMS03409, “as needed” retreatment with alemtuzumab could be offered to patients upon documented evidence of resumed MS disease activity, subject to safety-related disqualifications. The additional course(s) of alemtuzumab were administered at 12 mg/day on 3 consecutive days (36 mg total dose) at least 12 months after the prior treatment course. The benefits and risks of >2 treatment courses have not been fully established, but results suggest that the safety profile does not appear to change with additional courses.

The present study LPS13649 will provide long term safety and efficacy data on the patients who completed the extension study CAMMS03409, as well as on additional as-needed alemtuzumab retreatment. In addition, the study will provide information about the safety profile of patients who received other commercial DMTs following alemtuzumab treatment.

